8.7.4.2 VISIT 9 (DBPCFC Day 2)

Visit 9 will be conducted 1-4 weeks from visit 8. This visit entails Day 2 of the DBPCFC to CM, as per the trial DBPCFC SOPs. Participants will be monitored by a delegated clinician, supported by delegated nurse(s), and will remain in the department for up to 8 hours, as appropriate. In rare cases and if they experience severe anaphylaxis, they may need to be hospitalised overnight, as per the clinical judgment of the clinician.

- 1. Confirm continuation of participation.
- 2. Physical Examination, current medical history & vital signs: Weight, length, EASI Score & history of wheeze. The following will be confirmed to be normal and a statement to this effect recorded in the medical notes: general physical examination with chest auscultation, Peripheral arterial pulse, heart rate, systolic and diastolic blood pressure, respiratory rate, and oxygen saturation.
- 3. Collect diary from previous visit: Collect completed diary pages from previous visit and review. Any new AEs will be recorded in the participant's medical notes and on the AE Log and any previous AEs will be followed-up and marked as resolved if appropriate.
- 4. Demographics & review of medical history and diet: Details of any personal history of disease with focus on asthma, wheeze, urticaria and angioedema, atopic dermatitis, food allergies, and drug allergies. Concomitant medication
- 5. Challenge Day 2: Will be conducted as per the trial DBPCFC SOPs. Results of the DBPCFC must be recorded in the **participant's medical notes**. Unblinding of the challenge will take place as per the SOPs.
- 6. Record AEs: Any AEs occurring from this visit must be recorded in the participant's medical notes and on the AE Log (see section 10).
 - DBPCFC negative: Participants with a negative result to both days of the DBPCFC will be provided with advice for re-introduction of milk into the diet.
 - DBPCFC positive: Participants with a positive result to either day of the DBPCFC should be provided with clinical advice for ongoing CMA management at the clinician's discretion.
- 7. Collect any unused tins from parents: Collect any returned tins for destruction. Record returns and destruction in the appropriate accountability log.
- 8. Follow up communication: A follow-up communication (phone/email) will take place within 48 hours, as per the SOPs. Any late symptoms should be recorded in the participant's medical notes, and the clinician should assess if they are possibly associated with the challenge and record this in the participant's medical notes and transcribed onto the CRFs.

8.8 Procedures for assessing Efficacy

8.8.1 Efficacy assessment 1- Double blind food challenge

The DBPCFC to a specialised CM formula-based meal, provided by REACTA biotech, will take place at the end of the trial (V8 and V9). Briefly, this entails one day when the infants will be given a specialised CM-containing product in ascending doses, and one day where they will be given doses of a similar but non-CM-containing product (placebo). The challenge will be deemed positive if sufficient objective allergic symptoms are seen. Participants will be characterised according to their challenge outcome as CM protein-allergic (reaction on CM day but no reaction on placebo day), CM protein-tolerant (do not react on either the CM or the placebo day), or inconclusive (reacted in placebo day, did not finish challenge, etc). DBPCFC is the gold standard in the diagnosis of IgE-mediated food allergy and inherently entails use of placebo which minimises the potential for bias. This is not a proxy marker, but a well-established procedure used to rigorously characterise allergic individuals, and will be performed according to guidance provided to sites.

8.8.2 Other efficacy assessments

- 1. The dose at which reactivity occurs in the DBPCFC will be recorded in the participant's medical notes and will be used to assess changes in the tolerance threshold of participants who will react to the DBPCFC (Positive challenge still CM allergic participants).
- 2. The maximum wheal size of the Skin prick test to milk by calculating the longest wheal diameter [60] between visits 1 and 8 will be recorded and can be used as a proxy to asses changes in CM sensitisation in participants.
- 3. The titres of specific IgE levels to cows' milk casein, a-lactalbumin and b-lactoglobulin between visits 1 and 8 will be assessed by CAP FEIA [61] locally at the sites, will be recorded and can be used as a proxy to asses changes in CM sensitisation in participants.
- 4. EASI scores for eczema will be recorded at all face-to-face visits to assess changes in eczema activity.
- 5. Information on wheeze episodes, wheeze-related use of systemic steroids, and wheeze-related hospitalisations during last 12 months (in the first visit) and since the last visit (all other occasions) will be recorded at all face-to-face visits to assess differences between the study product-randomised arm and the routine care-randomised arm.
- 6. Information for physician-diagnosed allergies to other foods will be recorded on visits 1 and 9, to assess differences in the development of allergies to non-CM foods between participants.

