3.4.2 Secondary Outcomes/Endpoints

- 1. The dose at which reactivity occurs in the DBPCFC
- 2. The maximal wheal size of skin prick test to cows' milk
- 3. Specific IgE levels to cows' milk, casein, a-lactalbumin and b-lactoglobulin
- 4. EASI scores for Eczema
- 5. Wheeze (during last 12 months, use of systemic steroids, hospitalisations)
- 6. Doctor diagnosis of other food allergies
- 7. Height
- 8. Weight
- 9. Adverse events from the visit where infants are put on the study product (V3 for 'pHF tolerant' and V4 for 'pHF-reactive' CMA infants) to the final visit (V9)

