4 TRIAL DESIGN

This is a parallel-group, double-blind, randomised, normal-care-controlled trial that will evaluate the efficacy and safety of partially hydrolysed milk formula (pHF) freely fed to infants with moderate/severe CMA, in comparison to the current gold standard of feeding with extensively hydrolysed formula (eHF). At entry, patients with a history of CMA who meet specific criteria for moderate/severe CMA (Skin Prick Test (SPT) result to fresh CM of \geq 5mm or a CM-specific IgE blood value of \geq 2kU/L) and additional inclusion criteria will undergo a pHF food challenge and those who do not react will undergo an open challenge to normal CM formula to confirm that they are CM allergic. 'pHF tolerant, CM-allergic' infants (those that tolerated the pHF challenge but reacted to the CM challenge) will be randomised to receive either a free pHF or eHF diet (1:1 ratio) in a blinded manner for one year. Those that reacted to the pHF challenge ('pHF-reactive, CM-allergic' infants) do not need a CM challenge to confirm CM-allergy (reacting to pHF confirms CM allergy) and will be randomised for desensitisation by a blinded Oral Immunotherapy (OIT) protocol with either pHF or eHF (1:1 ratio), in order to be able to be freely fed with the respective formula after OIT. At the end of the pHF/eHF intervention, all infants will undergo a double-blind, placebo-controlled food challenge (DBPCFC) to CM which is the primary outcome of the trial, it will determine whether CMA has resolved and will uncover any differences in CM tolerance between the study groups.

There will be a two-stage internal pilot to assess the feasibility of recruitment. The first stage will last for 13 months from the date that the first site is opened to recruitment. At the end of that time, the following criteria will be assessed, and the study will continue unaltered if they are *all* met:

- 1) At least 20% of total sample size achieved (41 of the required 206 infants recruited)
- 2) At least 30% consent rate
- 3) Less than 20% drop-out rate

If fewer than 41 participants are recruited, ways to improve recruitment will be sought taking into consideration how much the recruitment falls short of the target: e.g. increasing number of recruiting sites, recruiting via additional pathways. If recruitment is significantly below expectations (less than 10% of the total required), terminating the trial will be considered.

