7 PARTICIPANT TIMELINE, ASSESSMENTS AND PROCEDURES

	V ₁	V ₂	V ₃	V_4	V 5	V ₆	TC1	V ₇	TC2	V ₈	V۹
	Screening visit	phf challenge	CM challenge ¹	1 st OIT Visit ²	2 nd OIT Visit ²	3 rd OIT Visit ²	Telephone call 1 ¹	Mid-study assessment	Telephone call 2 ³	1 st part DBPCFC to CM	2 nd part DBPCFC to CM
ACTIVITY		3-21 Ds from V1	2-28 Ds from V2	2-6 Ws from V2	4-6 Ws from Randomisation (V4) ⁴	8-12 Ws from Randomisation (V4) ⁴	12 Ws (+/- 2) from Randomisation (V3)	24 Ws (+/- 2) from Randomisation (V3 or V4)	36 Ws (+/- 2) from Randomisation (V3 or V4)	48 Ws (+/- 2) from Randomisation (V3 or V4)	1-4 Ws from V8
Informed consent signed	X										
Assessment of eligibility	х	х	x								
Confirmation of eligibility			x	х							
Demographics & review of medical history and diet ⁵	X										x
Assessment of Adverse events				Х	x	х	х	х	х	х	х
Physical Examination, current medical history & vital signs ⁶	X	x	x	X	х	X		х		x	x
Skin Prick Testing ⁷	Х									х	
Blood samples for antigen specific IgE ⁸	X									x	
Blood samples for safety markers ⁹	X										
Blood samples for storing ¹⁰	X							х		х	
Buccal samples for storing ¹¹		х						х		х	
Provide stool sample containers		x	(x)			Х		х			
Collection of stool samples for storing ¹²			х	Х				х		х	
Randomisation ¹³			(x)	х							
Dispensing of randomised			(x)	Х	х	х					
study product for home ¹⁴ Provide diary and instructions								v		v	
			(x)	X	X	X		X		X	
Collect and review Diary					X	X		X		X	X
Oral Immunotherapy (OIT)				X	X	X					
Oral Challenge and follow-up call		X	X							X	X
Telephone questions ¹⁵							х		х		

¹ Only applicable to participants with a negative reaction to pHF at V2.

² Only applicable to participants with a positive reaction to pHF V2.

³Telephone call 2 will take place for all participants 36 weeks (+/- 2w) after randomisation.

⁴ There must be at least 4 weeks between each of the OIT visits (V4, V5 and V6).

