8.4.1.2 VISIT 2 (Open Challenge to pHF)

Visit 2 will take place min: 3 days, max: 21 days after visit 1. Participants will be monitored by a delegated clinician, supported by delegated nurse(s), and will remain in the department for up to 8 hours, as appropriate. In rare cases and if they experience severe anaphylaxis, they may need to be hospitalised overnight, as per the clinical judgment of the clinician.

Participants will undergo the following assessments:

- 1. Physical Examination, current medical history & vital signs: Weight, length, EASI Score & history of wheeze. The following will be confirmed to be normal and a statement to this effect recorded in the medical notes: General physical examination with chest auscultation, Peripheral arterial pulse, heart rate, systolic and diastolic blood pressure, respiratory rate, and oxygen saturation.
- 2. Collection of buccal samples for storing: These will be collected only where **consent** has been provided, before the start of the challenge and stored locally until transferred to the central laboratory.
- 3. Open challenge to pHF: as per the trial SOPs. Results of the challenge must be recorded in the **participant's medical notes**.
- Reassessment of eligibility: A medically qualified doctor authorised on the site Delegation of Authority and Signature Log must confirm full eligibility of the patient for patients with a positive result at this challenge (see section 6). A record of this confirmation must be made in the patient's medical notes and appropriate CRF. In the event of weight loss during the trial screening period, randomisation may be postponed

until the required weight is achieved, providing all other inclusion criteria are met and visits fall within the required timeframes.

- Participants with a *negative* result at this challenge will proceed to VISIT 3 (Open Challenge to CM Formula).
- Participants with a *positive* result at this challenge will skip visit 3, and will proceed directly to VISIT 4 (OIT Visit 1).

Provide stool sample containers for the next visit: Provide eligible participants with containers for the collection of stool samples at home. Parents should take samples as close to the visit 3 (pHF tolerant participants) or visit 4 (pHF reactive participants) dates as possible, prior to the start of the challenge, and only from participants whose parents have provided **consent** for these additional samplings.

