After being screened at V1, potential participants need to meet the inclusion criteria to proceed to the free feeding (or the OIT module). **The assumptions for this stage are as follows: i.** We assume that no more than **25%** of the infants screened at V1 will meet the IgE or SPT inclusion criteria (conservative estimation). These infants will continue to the next step (pHF challenge-V2). **ii.** We expect that **~33%** of these infants will react to pHF at the pHF challenge–V2 [59], and will therefore be recruited as 'pHF– reactive, CM protein-allergic'. **iii.** From the remaining infants (those not reacting to pHF) we assume that **50%** will react to CM in the milk challenge–V3, and will therefore be recruited as 'pHF–tolerant, CM protein-allergic' (conservative assumption, as for this age range and these specific IgE levels, clinical reactivity is over 90% [69]).

The above conservative assumptions suggest that, for 206 infants to proceed to free feeding/OIT module, we need **1241 infants** to be reviewed at the screening visit-V1. 652 infants will reach V1 from the first recruitment pathway (Bounty). The remaining infants will be invited to V1 through the other recruitment pathways.

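### Section 8.8.2 assesses the reactive dose as a change among final-challenge reactors: a subset defined by the primary outcome, with no cow's milk baseline for the pHF-reactive stratum

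*Protocol*

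**What the plan says.** Protocol section 3.4.2 lists the first secondary outcome as "The dose at which reactivity occurs in the DBPCFC". That is a level at the final challenge.

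Section 8.8.2, item 1, then gives its use: it "will be used to assess changes in the tolerance threshold of participants who will react to the DBPCFC", and a bracket restates the group as those with a positive challenge who are still allergic. So the text adds two things: a change, and a restriction to reactors.

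The only cow's milk (CM) challenge before treatment is at V3. Section 4 says pHF-reactive infants "do not need a CM challenge to confirm CM-allergy (reacting to pHF confirms CM allergy"). Section 8.4.1.2 says they "will skip visit 3, and will proceed directly to" visit 4. The schedule in section 7 marks the CM challenge as "Only applicable to participants with a negative reaction to pHF at V2".

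Section 11.5 says primary and secondary outcomes follow intention to treat on all randomised participants, as far as practicable. Continuous data are analysed by two-sample t-test, or by Mann-Whitney if skewed.

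**The concern.** Reacting at the final challenge is, inconclusive results aside, the complement of the primary outcome. If pHF works, fewer pHF infants react, and those who still do may differ in baseline sensitivity from the eHF infants who do. Randomisation does not protect a comparison of reactive doses between those two groups. Section 9.1 itself suggests that resolution follows severity: it says pHF-tolerant infants may be more likely to outgrow the allergy.

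A change also needs a starting value on the same scale. One of the two randomisation strata has none. In the other, the V3 challenge is open and uses CM formula (section 4), while the final one is blinded and uses a specialised challenge meal (section 8.8.1).

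At stake is the first-listed secondary outcome, and what families of infants who remain allergic are told about reaction thresholds. A real benefit could be largely hidden, or could look like a lower threshold on pHF.

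**Working it through.** **1. Design inputs (section 11.3).** Tolerant proportions are 0.35 (eHF) and 0.60 (pHF), two-sided alpha 0.05, power 90%. With pooled variance and no continuity correction:

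n = [1.96·√(2·0.475·0.525) + 1.2816·√(0.35·0.65 + 0.60·0.40)]² / 0.25² = 81.8, so 82 per arm. Then 82/0.8 = 102.5, so 103 per arm and 206 in total. The stated figures reproduce.

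**2. Who enters a reactor-only comparison.** eHF: 0.65 × 82 = 53.3. pHF: 0.40 × 82 = 32.8. That is about 86 of 164 assessed infants.

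**3. Who has no CM baseline.** Section 11.3.1 expects that about 33% "of these infants will react to pHF at the pHF challenge–V2" and assumes that 50% of the rest react at V3. It calls the 50% conservative because "for this age range and these specific IgE levels, clinical reactivity is over 90" percent. With r the share reacting at V3:

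- r = 0.5: 0.33 / (0.33 + 0.67 × 0.5) = 49.6%, about 102 of 206
- r = 0.9: 0.33 / (0.33 + 0.67 × 0.9) = 35.4%, about 73 of 206

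At r = 0.5, and if resolution is equal across strata, reactors who also have a CM baseline number about 27 eHF and 17 pHF (43 of 164 before rounding by arm).

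**4. Size of the selection effect.** The protocol gives no threshold distribution. I assume a standard normal latent log-threshold, with infants above a top-dose cut-off c being tolerant. In eHF, c = z(0.65) = 0.385.

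Mean threshold among eHF reactors: -φ(0.385)/0.65 = -0.570. For the lowest 40% of a standard normal, with cut-off z(0.40) = -0.253: -φ(0.253)/0.40 = -0.966.

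- **A. pHF raises every threshold equally.** The shift needed for 60% tolerant is 0.385 + 0.253 = 0.639 SD. The reactor-only difference is 0.639 - 0.966 + 0.570 = **+0.243 SD**.
- **B. pHF makes only the least sensitive infants tolerant and leaves the rest unchanged.** The difference is -0.966 + 0.570 = **-0.396 SD**, although no infant was harmed.
- **C. Becoming tolerant is unrelated to threshold.** The difference is **0**, although 25 percentage points more pHF infants are tolerant.

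Simulated Mann-Whitney tests, 82 per arm:

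| Case | Reactors only, significant | All infants, tolerant ranked at top |
|---|---|---|
| A | about 36-38% (benefit) | about 95% |
| B | about 86-88% (apparent harm) | 43% |
| C | about 5% (chance) | 84% |

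**5. Between B and C.** Let the propensity to become tolerant on pHF correlate with threshold at ρ, keeping 60% tolerant. The simulated rate of significant apparent harm is:

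| ρ | Mean difference (SD) | Apparent harm |
|---|---|---|
| near 1 | -0.40 | up to about 88% |
| 0.7 | -0.21 | about 31% |
| 0.5 | about -0.15 | about 17% |
| 0.3 | -0.08 | about 8% |
| 0 | 0 | chance level |

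If pHF also raises all thresholds by 0.2 SD, apparent harm falls to about 7% at ρ = 0.7 and 4% at ρ = 0.5. At 0.4 SD it is 4% or less throughout.

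**The case against.** **Section 8.8.2 describes procedures, not the analysis.** Item 5 of the same list speaks of differences between arms and item 1 does not. A reactive dose exists only in infants who react, so naming them could be mere description, and section 11.5 keeps everyone in. Part of this stands: no test of reactors is spelled out, and how to rank or censor non-reactors may properly be left to the SAP. But item 1 is an efficacy assessment in a trial whose efficacy question is between arms, and it states both the population and the change. An SAP that did otherwise would contradict it.

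**The outcome is computable.** As listed in section 3.4.2 it needs no baseline, and every reactor has a value. This stands. Only the change in section 8.8.2 fails.

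**Apparent harm is an extreme case.** A reader might infer that the plan is biased against pHF, or will probably show false harm. The document does not support that. The 88% figure needs conversion to follow threshold perfectly and no general benefit. In case A the sign stays correct, and in case C there is no distortion. Section 9.1 says only that pHF-tolerant infants may resolve more readily.

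**Half without a baseline is not a fixed figure.** A reader might take it as one. It rests on the 50% V3 rate that the protocol calls conservative.

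**Challenge comparability cannot be fully judged.** Dose steps and units are in SOPs that are not shown. So the difference in material and blinding is a reason for doubt, not proof that a change score is invalid in the pHF-tolerant stratum.

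**Conclusion.** The point holds as a defect in a stated rule. Section 8.8.2, item 1, selects infants by a post-randomisation result, the primary outcome. It conflicts with the level in section 3.4.2 and with the all-randomised principle in section 11.5. It also asks for a change that has no CM baseline in the pHF-reactive stratum: 35% to 50% of those randomised, at 33% pHF reactivity.

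The selection is certain at the design rates (about 53 vs 33 reactors). Its effect on the estimate is not. Depending on how strongly resolution follows baseline sensitivity, it runs from no distortion, through attenuation (0.64 SD shown as 0.24 SD), to reversal (-0.40 SD). In none of the three cases worked through does the reactor-only comparison credit pHF with its full effect. All SD and power figures rest on the assumed normal latent threshold and 82 assessed infants per arm.

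This is a secondary outcome and the sample size is unaffected, so the change should be made but does not threaten the primary analysis.

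**What to change.** Reword section 8.8.2, item 1, and carry the wording into the SAP:

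- Compare the final CM-day reactive dose between arms in all randomised infants with a CM-day challenge.
- Treat infants who complete without reacting as right-censored above the top dose, or rank them above it. Use a dose-based survival model or a stratified rank or ordinal model, adjusted for initial pHF tolerance.
- State a rule for inconclusive challenges. For example, censor an unfinished CM day at the last tolerated dose, and run a sensitivity analysis for placebo reactors.
- Drop the reference to changes, or limit it to a descriptive summary in the pHF-tolerant stratum that notes the different challenge material and blinding.
- Keep the reactor-only dose summary as descriptive, without a test between arms.

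The cost is one reworded item and the matching SAP text. No new visits or data are needed, because the final challenge is already planned for every infant.

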8.9 Procedures for Assessing Safety

Safety will be assessed by the PI or delegated research staff actively monitoring and reporting all adverse events during the Active Monitoring Period (see section 10.1).

8.9.1 Safety Assessments

• At each trial visit, the following will be confirmed to be normal: general physical examination with chest auscultation, Peripheral arterial pulse, heart rate, systolic and diastolic blood pressure, respiratory rate, and oxygen saturation. In case any abnormality is observed, any further actions, including continuation, should be based on clinical judgement and GCP.

- Haematology and biochemistry blood tests will be confirmed as normal at visit 1. In case any abnormality is observed, any further actions, including continuation, should be based on clinical judgement and GCP.
- Weight and height will be measured in kg and cm with locally available equipment and recorded in the participant's medical notes during all visits to assess development of the infants.

8.10 Other Assessments

8.10.1 Special Assays or Procedures

Parents of participants will be asked if they consent to providing buccal samples, stool, and blood samples for future mechanistic research. All mechanistic samples will be sent to the University of Manchester once per year. All samples will remain the responsibility of the originating centre until a representative from the central laboratory has completed the relevant section of the Sample Transfer Log CRF. The samples will be collected and stored/managed as per the trial Laboratory manual. The Trial Manager will arrange for the appropriate shipment of the samples to the University of Manchester central laboratory.

